6.1.1.2 Body Temperature

The Sponsor will supply a thermometer to each subject along with directions for the use of the thermometer. Body temperature will be taken by subject twice a day (at approximately 12-hour intervals) from Day 1 to Day 8 (in the morning [between 6 and 10 AM, approximately] and in the evening [between 6 and 10 PM, approximately]) and it will be taken by site personnel at site at screening, Day 1 (prior to infusion), Day 2, Day 3, Day 5 and Day 8.

These results will be recorded in the diary or source document at site and transferred to the eCRF.

Body temperature will also be taken at site visits as indicated in [Table 1](#).

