10.2 Secondary Efficacy Analyses

The secondary efficacy endpoints will be analyzed on the ITTI and ITT populations. For time-to-event analyses of secondary efficacy endpoints, records on diary for suspicious ADE assessment and unscheduled assessment of site body temperature will be used together with data from regular scheduled assessment.

- The following secondary efficacy endpoints will be analyzed using a Kaplan Meier model to assess differences between placebo and CT-P27. Missing time of completion of diary will be considered as described in the section for the primary efficacy endpoint:

- Time (in days) to resumption of normal activity as reported in Domain 2 of the Flu-iiQ™: [Start date/time of resumption of normal activity] – [Start date/time of study drug administration]

The resumption of normal activity has occurred if the degree of difficulty of all of the Domain 2 items are of no difficulty or some difficulty for at least 24 hours.

- Time (in days) to return to normal body temperature (<37.0°C) for at least 24 hours : [Start date/time of resolution of fever] – [Start date/time of study drug administration]

Data of body temperature recorded on the diary as well as the ones measured from the sites will be used to determine the return time to normal body temperature for at least 24 hours.

However, assessments which exceeds 24 hours measurement interval will be excluded because of lack of consecutiveness in determining the resolution.

If time of measurement of body temperature from site is missing, then the time will be imputed based on time of study drug administration such that missing body temperature assessment time on Day 3 will be imputed as: Infusion time + 48 hours. Missing times on other days will be imputed in the same manner.

- Time to resolution of individual symptoms for at least 24 hours as reported in Domain 1 of the Flu-iiQ™: [Start date/time of resolution of individual influenza symptoms] – [Start date/time of study drug administration]

The resolution of individual influenza symptoms will be determined as described for the primary efficacy endpoint.

- Severity of symptoms as recorded on the Domain 1 of the Flu-iiQ™
 - Impact of influenza symptoms consist of 4 scales of the items in Domain 1 (respiratory symptoms, constitutional symptoms, systemic symptoms, total symptoms)
 - Respiratory symptoms: cough, sore throat, and nasal congestion

Statistical Analysis Plan

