Missing body temperature from diary will not be imputed, but when 3 subsequent time points have only missing value for middle of the time points and subject data indicates resolution of fever at the other two time points, then it can be considered that fever has resolved. The following examples should be used for reference:

- a. Example 1: Resolution of fever is considered to be maintained for 24 hours

Day 1 morning (10NOV16, 9:00 AM) Resolved
Day 1 evening (10NOV16, 9:00 PM) Missing
Day 2 morning (11NOV16, 9:00 AM) Resolved

- b. Example 2: Resolution of fever is not considered to be maintained for 24 hours

Day 1 morning (10NOV16, 9:00 AM) Resolved
Day 1 evening (10NOV16, 9:00 PM) Missing
Day 2 morning (11NOV16, 9:00 AM) Missing
Day 2 evening (11NOV16, 9:00 PM) Resolved

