10.3.2 Missing Data Handling for Secondary Efficacy Analyses

10.3.2.1 Time to Resumption of Normal Activity as Reported in Domain 2 of the Flu-iiQ™

If the number of missing items on Domain 2 is less than half of the total number of items on the domain, missing values will be replaced by 0 (same rule as 2-1 in section 10.3.1). Otherwise, it cannot be considered

Statistical Analysis Plan

that normal activity is resumed.

10.3.2.2 Time to Return to Normal Body Temperature (<37.0°C) for at Least 24 hours

Missing body temperature from diary or sites will not be imputed. However when there are missing values between two time-points with interval 24 hours at which normal body temperature are reported, it can be considered that fever is resolved for 24 hours.

10.3.2.3 Time to Resolution of Individual Symptoms for at Least 24 hours as Recorded on the Flu-iiQ™

The same rule for missing body temperature described in section 10.3.1 will be applied.

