16. Sponsor-supplied or agreed in advance rapid influenza diagnostic test material will be used. And if there is available test result confirmed as influenza A prior to obtaining written informed consent and that result was from the influenza diagnostic test which is agreed with Sponsor in advance, that test result can be allowed. At screening, testing must be performed within 24 hours before study drug administration. Subjects with a negative test result by rapid diagnostic test, who have onset of symptoms within 48 hours (window of +12 hours is allowed) before study drug administration, can be rescreened only once.
17. The Investigator or designee will perform a symptom-directed physical examination (which should include, at a minimum, the examination of ear, nose, throat, sinuses, and lungs) and assessment for potential complications of influenza.
18. The subject will record the results of the Flu-iiQ™ in the diary.
 - Flu-iiQ™ will be recorded once by the subject at the screening visit and will be recorded twice a day (at approximately 12-hour intervals) from Day 1 to Day 8 (in the morning [between 6 and 10 AM, approximately] and in the evening [between 6 and 10 PM, approximately]).
19. Body temperature which a subject experiences in prior to screening will be collected and body temperature taken with any type of thermometer will be acceptable. However, from the screening period, Sponsor-supplied thermometer will be used.
 - Temperature will be measured by subject; It will be recorded twice a day (at approximately 12-hour intervals) from Day 1 to Day 8 (in the morning [between 6 and 10 AM, approximately] and in the evening [between 6 and 10 PM, approximately]).
 - Temperature will be measured by site personnel at site: at screening, Day 1 (prior to infusion), Day 2 (±4 hours), Day 3 (±4 hours), Day 5 (±4 hours) and Day 8 (±4 hours).
 - These will be used for assessment of endpoint.
20. Use of all medications, from 30 days prior to randomization and up until Day 110/EOS visit, will be recorded in the subject's eCRF.
21. AEs will be collected from the date the informed consent form is signed until Day 110/EOS visit.
22. EOS visit will be done at Day 110. But if a subject is early terminated from the study, EOS visit will be done to assess safety parameters at any time.

CONFIDENTIAL

37/62 page

Effective Date: 01-Aug-2018

Statistical Analysis Plan

Schedule of Assessments (Unscheduled Visits Subjects with Suspicious ADE)

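### Secondary fever endpoint: after one missed reading, a gap slightly over 24 hours breaks an all-normal run and makes the resolution time at least a day late, or censors it

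*SAP*

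**What the plan says.** SAP section 10.2 defines the secondary fever endpoint as the time from the start of dosing to the start of a period below 37.0°C that lasts at least 24 hours. It draws on two sources: "Data of body temperature recorded on the diary as well as the ones measured from the sites will be used". It then limits how readings may be chained: "assessments which exceeds 24 hours measurement interval will be excluded because of lack of consecutiveness in determining the resolution".

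Section 10.3.2.2 says that missing temperatures are not imputed, but fever may be taken as resolved "when there are missing values between two time-points with interval 24 hours at which normal body temperature are reported". Neither section gives a tolerance or says whether 24 hours means scheduled or clock time.

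The protocol (6.1.1.2) has subjects measure temperature "in the morning [between 6 and 10 AM, approximately] and in the evening [between 6 and 10 PM, approximately". SAP 14.1 repeats these windows. Post-dose site temperatures are scheduled on "Day 2 (±4 hours), Day 3 (±4 hours), Day 5 (±4 hours) and Day 8 (±4 hours").

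For the primary endpoint, section 10.3.1 uses a different rule. It treats fever as resolved "when 3 subsequent time points have only missing value for middle of the time points" and the two outer readings are normal. That rule goes by position in the schedule and sets no upper limit in hours. Section 10.3.2.3 applies it to individual symptoms as well.

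Section 10.1 sets a missing diary time to 10:00 AM or 10:00 PM, and section 10.2 carries this over to the secondary time-to-event endpoints.

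**The concern.** The endpoint combines a 24-hour minimum for the run with a 24-hour maximum for each interval inside it. The readings themselves are scheduled to within about 4 hours. With a complete diary this does no harm, because intervals are about 12 hours. With one reading missed, the two neighbours come from the same slot on consecutive days, and whether their gap exceeds 24 hours depends on minutes of clock time, not on fever.

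At stake is the start time on this one secondary endpoint. A subject whose recorded temperatures are all normal can be given a return to normal more than a day late, or be censored. For the same gap in the same diary, the primary analysis would keep the run intact.

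**Working it through.** The plan gives no figure for this point. Its own worked examples in SAP 10.3.1 do fix the geometry: Example 1 (normal, missing, normal; 9:00 AM to 9:00 AM) spans 24 h and counts, and Example 2 (two missing; 9:00 AM to 9:00 PM next day) spans 36 h and does not.

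**Inputs**
- Windows 6–10 AM and 6–10 PM (protocol 6.1.1.2, SAP 14.1).
- Minimum run 24 h; maximum interval 24 h (SAP 10.2).
- Missing diary time set to 10:00 (SAP 10.1).
- Assumed: readings stay inside the windows, and the later clock time is as likely to be later as earlier than the previous day's.

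**Step 1: gap after one missed reading.** Gap = 24 + (later clock time − earlier clock time). Minimum 24 + (6 − 10) = 20 h; maximum 24 + (10 − 6) = 28 h.

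**Step 2: rule of 10.2 applied.** The start is taken as the first normal reading from which every interval is at most 24 h and the run reaches at least 24 h. The first normal reading is at 0 h, the next is missed, and normal readings follow every 12 h after the gap.

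| Gap (h) | Run up to the next reading | Shift of start, 10.2 | Shift of start, 10.3.1 rule |
|---|---|---|---|
| 20 | 20 + 12 = 32 h, intact | 0 | 0 |
| 22 | 34 h, intact | 0 | 0 |
| 23.5 | 35.5 h, intact | 0 | 0 |
| 24 | intact | 0 | 0 |
| 24.25 | broken | 24.25 h | 0 |
| 26 | broken | 26 h | 0 |
| 28 | broken | 28 h | 0 |

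**Step 3: share and mean shift.** By symmetry, P(gap > 24 h) = 1/2. If many subjects record identical rounded times on both days, it is (1 − P(tie))/2, which is lower. With times uniform in a window of width W, the mean gap among those over 24 h is 24 + W/3. For W = 4 h that is 24 + 1.33 = 25.3 h; for W = 0.5 h it is 24.2 h.

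**Step 4: a later miss.** If the first two readings (morning, evening) are normal and the next morning is missed, the run so far spans only 8 to 16 h. A gap over 24 h from that evening to the next moves the start from the first morning to the second evening: 36 ± 4 = 32 to 40 h. Once the run already spans 24 h, a miss changes nothing.

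**Step 5: site readings.** Normal readings at 0, 25 and 37 h, with a normal site reading at 6 h, have intervals of 6, 19 and 12 h, so the start stays at 0. No site temperature is scheduled on Days 4, 6 and 7, so exposure lies mainly around those days.

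**Step 6: end of diary.** Take Day 7 morning normal (0 h), Day 7 evening missed, Day 8 morning normal (24.5 h) and Day 8 evening normal (36 h). The first interval is broken and the remaining run is 36 − 24.5 = 11.5 h. With no other reading available, the subject is censored.

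**Step 7: the 10:00 rule.** An earlier reading at 09:00 followed by a same-slot reading with no recorded time gives 24 + (10 − 9) = 25 h. Any earlier reading before 10:00 gives a gap over 24 h. If instead the earlier time is the missing one, the gap is 24 h or less, so the imputation can act in either direction.

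**The case against.** The best defence is that section 10.3.2.2 means 24 hours on the schedule grid. Example 1 in 10.3.1 runs from 9:00 to 9:00, and on that reading one missed reading is bridged for this endpoint too. The text allows this. But section 10.2 states its exclusion separately, and the endpoint is built from recorded or imputed clock times. A possibly nominal phrase in 10.3.2.2 does not override an explicit exclusion. If nominal time was meant, the SAP needs to say so.

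It is also fair that the limit is deliberate, has a stated reason (readings should be consecutive), applies alike to all arms and touches one secondary endpoint. Nothing here shows bias between arms. Site readings, including unscheduled ones, and diaries kept for suspected antibody-dependent enhancement will rescue some runs. The primary and secondary fever times can also differ by design, because the primary uses diary temperatures only, so a difference alone is not a fault.

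Three stronger inferences fail:
- **That only a gap of exactly 24 hours works**, with a chance of 1/240, or 0.4%, at minute precision. This judges the two flanking readings alone. Gaps of 20 to 24 h keep the same start once the next normal reading arrives.
- **That half of all three-reading runs are lost** because they span slightly under 24 h by the clock. The next normal reading extends such a run and the start does not move; an event is lost only if no later reading exists.
- **That 24 hours should be redefined as at least 20 h by clock for every criterion.** This would relax the protocol's definition, including that of the primary endpoint, and is not needed to repair a bridging rule.

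**Conclusion.** The point holds in limited form. As written, section 10.2 can break a run of entirely normal recorded temperatures on the secondary fever endpoint. Three conditions must coincide: a missed reading before the run spans 24 h, a resulting gap over 24 h, and no site reading that splits the gap.

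About half of single-miss gaps meet the second condition if clock times vary symmetrically within the windows, which is an assumption; ties would lower the share. The shift is then at least 24 h: 24 to 28 h when the miss directly follows the first normal reading (mean 25.3 h under uniform times), and more when it comes later. Near Day 8 the event may be censored instead.

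The effect on the group result cannot be stated, because the documents give no rate of missed diary readings. The point is minor in weight, but the rule is internally awkward and inconsistent with the SAP's own treatment of the primary endpoint.

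**What to change.** For this secondary endpoint only, replace the 24-hour exclusion in section 10.2 and the 24-hour interval wording in 10.3.2.2 with the position-based rule of 10.3.1. One missed scheduled reading between two normal readings is bridged (gap up to 28 h), and two or more consecutive missed readings still break the run. The cases separate cleanly: two misses leave 36 ± 4 = 32 to 40 h. Any recorded reading of 37.0°C or above inside the gap, from diary or site, should still break the run.

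Leave the protocol's minimum of 24 hours and the primary endpoint unchanged.

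The cost is a change of SAP wording, one programming rule, and acceptance of an unobserved interval of up to 28 h. The protocol's analysis section for this endpoint (8.5.2) contains no such interval limit, so its text need not change.

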4.3.1 Inclusion Criteria

Each subject must meet all the following criteria to participate in this study:

1. Subject is a male or female and aged 19 to 64 years, inclusive.
2. Subject can voluntarily provide a written informed consent.

3. Onset of illness no more than 48 hours prior to the planned administration of study drug. If the adjustments of visit schedule is required, additional 12 hours can be allowed (Maximum onset of illness: 60 hours).

Note: time of onset of illness is defined as the earlier of either (a) the time when the body temperature was first measured as $\geq 38.0^{\circ}\text{C}$ ($\geq 100.4^{\circ}\text{F}$) or (b) the time when the subject experienced the presence of at least two symptoms that are respiratory and/or constitutional (moderate to severe in intensity).

4. As reported by the subject and recorded on the Flu-iiQ™ completed at screening, the subject has at least two of the following symptoms (moderate to severe in intensity):
 - a) Respiratory symptom (cough, sore throat, or nasal congestion) or
 - b) Constitutional symptom (headache, feeling feverish, body aches and pains, or fatigue).
5. Subject has a fever $\geq 38.0^{\circ}\text{C}$ or $\geq 100.4^{\circ}\text{F}$ at screening or a history of fever within the 24 hours prior to screening and has received treatment with an antipyretic(s) in the 6 hours prior to screening.
6. Subject is diagnosed with influenza A at screening, using the Sponsor-supplied or agreed in advance rapid influenza diagnostic test. And if there is available test result confirmed as influenza A prior to obtaining written informed consent and that result was from the influenza diagnostic test which is agreed with Sponsor in advance, that test result can be allowed
7. For both male and female subjects, the subject and his/her partner (if of childbearing potential) agree to use a highly effective method of contraception during the study and for 5 months after the administration of study drug.
 - a) Male and female subjects and their partner who have been surgically sterilized for less than 6 months prior to the date of informed consent must agree to use a highly effective method of contraception during the study and for 5 months after the administration of study drug.
 - b) Menopausal females must have experienced their last menstrual period more than 12 months prior to the date of informed consent to be classified as not of childbearing potential.

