10.1 Primary Efficacy Analysis

The primary efficacy endpoint analysis will assess the time from the administration of study drug to resolution of influenza symptoms and fever. The Flu-iiQ™ and body temperature recorded in diary including records as

Statistical Analysis Plan

a part of suspicious ADE assessment will be used for the analysis. The Flu-iiQ™ is a validated questionnaire with four domains. This includes the Domain 1; intensity of influenza symptoms, Domain 2; impact on activities, Domain 3; effects on feelings and Domain 4; concerns due to influenza. Subjects are offered four choices, ranging from the most positive response (e.g., none or not at all) to the most negative choice (e.g., severe or great difficulty). This analysis will be performed on the ITTI population.

The definitions of resolution of influenza symptoms and fever are described below.

Resolution of symptoms has occurred if all of the following influenza symptoms (as recorded on the Flu-iiQ™ of Domain 1) are mild in intensity or none for at least 24 hours. (4-point scale - 0: None, 1: Mild, 2: Moderate, 3: Severe).

- Respiratory symptoms (cough, sore throat, and nasal congestion)
- Constitutional symptoms (headache, feeling feverish, body aches and pains, and fatigue)

Resolution of fever is defined as:

- Body temperature (as recorded in the diary) of $<37.0^{\circ}\text{C}$ for at least 24 hours.

The start time for resolution of influenza symptom and fever is defined as the start time when symptoms and fever are resolved, whichever occurred latest.

The time (in days) from the administration of study drug to resolution of influenza symptoms and fever will be calculated as follows: [Start date/time of resolution of influenza symptoms and fever] – [Start date/time of study drug administration]. If time of completion of diary for Flu-iiQ™ and body temperature is missing then the time will be assumed to be 10:00 AM and 10:00 PM for Morning and Evening, respectively.

If the subject has received the drugs for symptom relief, the effective duration of the drugs for symptom relief should be considered in determining the start time for resolution of symptom and fever.

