Viral shedding (titers) of swab samples based on qPCR and cell culture will be evaluated at the scheduled collection times. The listing will include titer results, whether the influenza A is confirmed and Area under the Curve (AUC) of viral loads. However, since cell culture results have information of both influenza A and B, the listing and tables for cell culture will present analysis results regardless of influenza type. Changes in viral shedding will be assessed as the change from baseline in \log_{10} vp/mL and \log_{10} TCID₅₀/mL for qPCR and cell culture respectively. If viral loads are lower than LLoQ (2.18 for qPCR), they will be treated as value without inequality sign. Whereas viral load lower than LLoQ for cell culture (0.75) will be considered as negative value and a negative value will be treated as 0. If the subtype of influenza A is "H1", "NA" or "Unknown", the virus titer from HA assay will be used for cell culture analysis. Otherwise, if the subtype is "H3", the virus titer from NP ELISA will be used.

These will be summarized for each treatment group and collection time.

The following analyses will also be performed:

- Summary of viral shedding results; percentage of subjects with positive/negative viral shedding at each visit (baseline, day 2, 3, 5, 8)
- Duration (in days) of viral shedding; from date/time of baseline assessment to last positive sample. Subjects with at least one positive sample after baseline will be included in the summary.

Statistical Analysis Plan

- AUC of viral levels; from date of baseline assessment to last measurable value of subjects who have at least one post-baseline result (including BLQ (Below the Limit of Quantification) and negative values). If there are BLQ or missing values between measurable values, they are assumed to fall linearly between measurable values.
- Change from baseline in descriptive statistics of viral shedding of Swab Samples; descriptive statistics of actual value and change from baseline for viral shedding of swab samples will be presented by treatment group at each visit.
- Mean viral load titer (log values)
Mean viral load titer for each scheduled time point will be plotted with the SD of mean value.

- Incidence of secondary complications of influenza

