14.2.1.1	ITTI	Summary of Time to Resolution of Influenza Symptom and Fever	Listing 16.2.1.3 End of Study, Listing 16.2.5.1 Study Drug Administration, Listing 16.2.6.1 Flu-iiQ, Listing 16.2.6.2 Body Temperature from Diary
14.2.1.2	ITTI	Summary of Time to Resolution of Influenza Symptom and Fever (Imputation)	Listing 16.2.1.3 End of Study, Listing 16.2.5.1 Study Drug Administration, Listing 16.2.6.1 Flu-iiQ, Listing 16.2.6.2 Body Temperature from Diary
14.2.1.3	ITTI	Summary of Time to Resolution of Influenza Symptom and Fever - Sensitivity Analysis (Tipping Point Analysis)	Listing 16.2.5.1 Study Drug Administration, Listing 16.2.6.1 Flu-iiQ, Listing 16.2.6.2 Body Temperature from Diary
14.2.1.4	ITTI	Summary of Time to Resolution of Influenza Symptom - Sensitivity Analysis	Listing 16.2.1.3 End of Study, Listing 16.2.5.1 Study Drug Administration, Listing 16.2.6.1 Flu-iiQ

CONFIDENTIAL

51/62 page

Effective Date: 01-Aug-2018

Statistical Analysis Plan

14.2.1.5	ITTI	Summary of Time to Resolution of Influenza Symptom and Fever (<37.8°C) - Sensitivity Analysis	Listing 16.2.1.3 End of Study, Listing 16.2.5.1 Study Drug Administration, Listing 16.2.6.1 Flu-iiQ, Listing 16.2.6.2 Body Temperature from Diary
14.2.2.1	ITT	Summary of Time to Resumption of Normal Activity - Kaplan-Meier Model	Listing 16.2.1.3 End of Study, Listing 16.2.5.1 Study Drug Administration, Listing 16.2.6.1 Flu-iiQ
14.2.2.2	ITTI	Summary of Time to Resumption of Normal Activity - Kaplan-Meier Model	Listing 16.2.1.3 End of Study, Listing 16.2.5.1 Study Drug Administration, Listing 16.2.6.1 Flu-iiQ
14.2.3.1	ITT	Summary of Time to Resolution of Fever - Kaplan-Meier Model	Listing 16.2.1.3 End of Study, Listing 16.2.5.1 Study Drug Administration, Listing 16.2.6.2 Body Temperature from Diary, Listing 16.2.9.1 Vital Signs and Body Temperature
14.2.3.2	ITTI	Summary of Time to Resolution of Fever - Kaplan-Meier Model	Listing 16.2.1.3 End of Study, Listing 16.2.5.1 Study Drug Administration, Listing 16.2.6.2 Body Temperature from Diary, Listing 16.2.9.1 Vital Signs and Body Temperature
14.2.4.1	ITT	Summary of Time to Resolution of Individual Influenza Symptom - Kaplan-Meier Model	Listing 16.2.1.3 End of Study, Listing 16.2.5.1 Study Drug Administration, Listing 16.2.6.1 Flu-iiQ
14.2.4.2	ITTI	Summary of Time to Resolution of Individual Influenza Symptom - Kaplan-Meier Model	Listing 16.2.1.3 End of Study, Listing 16.2.5.1 Study Drug Administration, Listing 16.2.6.1 Flu-iiQ

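### Time to resolution of each individual symptom includes subjects who never had that symptom above mild, which dilutes the estimated effect and pulls the Kaplan-Meier medians together

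*SAP*

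**What the plan says.** The population is set in SAP 10.2: "The secondary efficacy endpoints will be analyzed on the ITTI and ITT populations". Time to resolution of individual symptoms is one of the endpoints that "will be analyzed using a Kaplan Meier model to assess differences between placebo and CT-P27", timed from the start of study drug.

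The event is borrowed from the primary analysis: "The resolution of individual influenza symptoms will be determined as described for the primary efficacy endpoint". In SAP 10.1 symptoms count as resolved when they "are mild in intensity or none for at least 24 hours". No earlier moderate or severe score is required.

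Protocol 4.3.1 asks that "the subject has at least two of the following symptoms (moderate to severe in intensity"). Seven symptoms are listed, so an eligible subject may have up to five at none or mild.

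Nothing elsewhere narrows the population:

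- SAP 10.3.2.3 deals only with missing records: "The same rule for missing body temperature described in section 10.3.1 will be applied".
- SAP 14.7 lists "Summary of Time to Resolution of Individual Influenza Symptom - Kaplan-Meier Model" once for ITT (14.2.4.1) and once for ITTI (14.2.4.2).
- SAP section 13, on changes from the protocol, does not mention the point.

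For duration of viral shedding, by contrast, SAP 10.2 does limit the summary: "Subjects with at least one positive sample after baseline will be included in the summary".

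**The concern.** The primary rule works for the primary endpoint because that endpoint needs all seven symptoms and fever to resolve together. Every eligible subject has at least two symptoms at moderate or severe at screening, so every subject starts unresolved. When the rule is applied to one symptom at a time, that guarantee is lost.

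A subject who never has the symptom above mild meets the definition at about the first post-dose diary record, or later if the symptom-relief drug rule in SAP 10.1 moves the start. That subject had nothing to recover from. The resulting curve mixes recovery with absence of the symptom. A block of very early events in every arm shrinks the difference between arms and lowers both medians. The SAP (1.1) says the trial is to supply effect-size information for later studies, so symptom curves that understate the effect in affected subjects could mislead that work.

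**Working it through.** **The plan's own figure.** The documents give no power for this endpoint. The primary figure in SAP 5.2 (63 vs 38, 1.8 days, SD 3, two-sided 5%, Wilcoxon) reproduces:

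- SD adjusted for rank-sum efficiency: 3/√(3/π) = 3.070.
- SE = 3.070 × √(1/38 + 1/63) = 3.070 × 0.2054 = 0.631.
- Power = Φ(1.8/0.631 − 1.96) = 81.4%, against the stated 80%.
- Enrolment: 164/0.9 = 182.2, rounded up to 183, as stated.

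**Limit set by the entry rule.** At most 5 of 7 symptoms, 71.4% averaged over symptoms, can be none or mild at screening. This is a logical ceiling, not an expected share.

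**Dilution of the mean.** Let p be the share never above mild on a symptom and Δ the mean difference among the others. If the symptom-free resolve at the same time in both arms, the mean difference in all subjects is (1 − p)Δ. With an assumed Δ of 3.0 − 2.2 = 0.8 day, this is 0.64 day at p = 20%, 0.48 at 40% and 0.32 at 60%.

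**Medians.** If p is at least one half in an arm and those subjects qualify at the first record, the Kaplan-Meier curve is at or below 0.5 there. The median is then the first record, whatever the drug does.

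**Power, all subjects against the restricted set.** Assumptions, none from the documents except the group sizes: gamma times with means 2.2 vs 3.0 days and SD 2.2; symptom-free subjects at 0.3 day in both arms; rank-sum test, 63 vs 38.

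| Symptom-free | All subjects | Restricted | Gain |
|---|---|---|---|
| 20% | 44% | 58% | 14 points |
| 40% | 26% | 45% | 19 points |
| 60% | 13% | 29% | 16 points |

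Repeat runs agree to within about 3 points. The difference in medians for all subjects falls from 0.97 day with no symptom-free subjects to 0.64 at 40% and 0 at 60%.

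**Second set of assumptions, log-rank test.** Means 5.0 vs 3.2 days, SD 3, 12-hour diary grid, censoring at 7 days, symptom-free subjects at 0.5 day:

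| Symptom-free | Power, all | Power, restricted | Medians, all (placebo vs active, days) |
|---|---|---|---|
| 20% | 62% | 71% | 4.0 vs 2.0 |
| 40% | 45% | 62% | 2.5 vs 1.0 |
| 50% | 37% | 51% | 0.5 vs 0.5 |
| 71% | 23% | 33% | 0.5 vs 0.5 |

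The restricted medians stay at 4.5 vs 2.5 days throughout. Here the gain is 9 to 17 points.

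**Type I error.** With no drug effect and equal shares in both arms, the all-subjects rank-sum test rejected in about 4 to 6% of simulated trials at every share tried.

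**The case against.** Keeping all randomised subjects is defensible, and the comparison remains a valid test. Several points on this side stand.

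- **The gain is smaller than it may look.** A reader might set the 67% power obtained when everyone has the symptom against 26% at 40% symptom-free, and infer that the restriction recovers 41 points. It cannot, because it drops the symptom-free subjects. The restricted analysis reaches 45%, a gain of 19.
- **Chance imbalance is not a separate source of false positives.** A reader might infer that unequal symptom prevalence at baseline would pass for a drug effect. It could in a given trial: with no drug effect and symptom-free probabilities set at 50% and 30%, 39% of simulated trials gave p < 0.05. But under randomisation, with 40% symptom-free overall, the difference in shares has SD √(0.4 × 0.6 × (1/38 + 1/63)) = 10.1 points. A 20-point gap is about two SDs, and such gaps are already within the nominal 5%.
- **The shares are unknown.** Absence of about half or more is implausible for some symptoms. Entry requires fever, or recent fever with antipyretic use, so most subjects will probably report feeling feverish.
- **A baseline filter loses some information.** Subjects are dosed within 48 hours of onset (60 at most). A symptom that is mild at baseline may worsen after dosing; such a subject does not resolve at the first record and is informative.
- **The test is assumed.** SAP 10.2 specifies a Kaplan-Meier model and names no test for this endpoint.
- **Other symptom analyses exist.** SAP 10.2 also plans scale scores, symptom AUC and the incidence of Grade 2 or higher symptoms. These lessen reliance on the curves but do not correct them.

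The smaller-n objection does not stand: the restricted analysis had more power in every scenario with symptom-free subjects.

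**Conclusion.** The point holds as a loss of sensitivity and interpretability in a secondary endpoint. As written, the SAP counts subjects who never had a symptom above mild as early recoveries from it. This dilutes the effect and pulls the medians together, without inflating type I error.

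Under the illustrative assumptions, restriction gains roughly 14 to 19 points of power with the rank-sum test and 9 to 17 with the log-rank test. The true size depends on the share lacking each symptom, which the documents do not give. The near-zero median difference once about half lack the symptom needs no effect-size assumption.

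The same logic applies to resumption of normal activity. SAP 10.2 counts it as reached when every Domain 2 item is at no or some difficulty, and no entry criterion requires impaired activity. Its size is not quantified here.

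A reader might infer that the primary result or the sample size is compromised. The documents do not support that: the primary endpoint needs all seven symptoms and fever resolved, every eligible subject starts with at least two qualifying symptoms, and this secondary endpoint has no power claim of its own.

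**What to change.** In SAP 10.2, define the main Kaplan-Meier analysis of each symptom as the subjects who score moderate or severe on that symptom on the baseline Flu-iiQ, and show n per arm. The filter must use the baseline record. It then selects on a pre-dose variable and keeps the comparison randomised; selecting on whether the symptom ever exceeded mild would use post-dose data.

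Keep the full ITTI and ITT tables (14.2.4.1 and 14.2.4.2) as supportive, so that symptoms first reaching moderate or severe after dosing are still captured, and say so in the text. Treat resumption of normal activity the same way, with at least one Domain 2 item worse than some difficulty at baseline.

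The cost is SAP wording, a filter on screening data already collected and additional tables. The downside is a smaller n per symptom, which will differ between symptoms.
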